2 STUDY SUMMARY

Background: Hemiplegic Cerebral Palsy (HCP) causes lifelong weakness and stiffness of one side of the body, impacting everyday functioning. Most affected children do not have access to effective intensive upper limb therapy.

Aim: To determine whether a wrist-worn device and software (including a smartphone application), incorporating positive feedback and peer support, can encourage increased use of the affected arm and hand during everyday activities.

Study design: Proof of concept study

Methods:

Participants: 20 children aged 8-18 years with HCP, their age-matched controls ("Buddies"), therapists and family members. The children with HCP will be recruited by clinicians at Newcastle upon Tyne Hospitals Trust and at the Evelina London Children's Hospital and through local self-help groups. The children will each nominate and approach their potential "buddy", who will then decide with their family whether they wish to learn more about the study and contact the research team if this is the case.

Intervention: Baseline (2 weeks): the device records arm activity without giving feedback. Active feedback (6 weeks): the device records and gives feedback (through the app) as well as personalised prompts during the day based on encouraging arm activity if this falls below a pre-set personalised threshold. Final (2 week) period: as for baseline.

Assessment:

At the start of the study the children will take part in a range of standardised hand and arm assessments conducted by an experienced occupational therapist. This will include the Assisting Hand Assessment (AHA) or equivalent Ad-AHA (age 13 years+), the Tyneside Pegboard Test (manual dexterity) and the ABILHAND-Kids questionnaire. Proof of concept assessment will be quantitative, produced by the data collected from the accelerometer with regards to the level of arm activity. In addition, there will be a qualitative component, via weekly meeting by phone/Skype/face to face. This will help to understand the acceptability and feasibility of implementation of the device and help with troubleshooting.

Analysis: We will assess feasibility and, through discussion with families, "Buddies" and therapists, acceptability. Hand function will be assessed at baseline. Changes in arm activity (derived from accelerometer data in the devices) will be analysed using single case experimental design for proof of concept that the approach can increase use of the affected upper limb.

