6.1.4 Intervention

All children/young people taking part in the study will wear a device on each wrist, containing an accelerometer and sending data through Bluetooth linking to a smartphone application which can derive information on the activity of each arm. The devices are similar to a Fitbit and are CE tested activity trackers.

The children/young people will also borrow a smartphone for the course of the study if they do not already have one. If they do have a smartphone which is of adequate specification, the app will be downloaded on to their smartphone.

We will make sure the children/young people and families are provided with information/education about safe internet use as part of the project. Currently available suitable sources of information include the Safer Internet Centre (www.saferinternet.org.uk/advice-centre/young-people/resources-11-19s) which has suitable resources; and the Online Safety Guide from Internet Matters: https://www.internetmatters.org/advice/online-safety-guide.

The children/young people and families will be provided with instructions regarding the use of the app and phone, as well as on charging the devices. These instructions will be finalised at the end of the current development phase of the research. We will check that they understand the instructions and can carry them out. We will also provide them with contact details in case they have any questions or difficulties.

The children/young people will wear the wristbands all day each day for the 10 week period, one on each wrist. They will be removed at night, and for charging, and for activities which might be detrimental to the devices such as swimming, washing etc.

During the first 2 weeks, the devices will record arm activity but will not provide any hourly prompts to move. There will also not be any personalised feedback through the app. The aim of the first 2 weeks is to obtain baseline data on activity levels for each young person.

Personalised thresholds for activity levels will then be set, based on this baseline data and after negotiation with the children/young people and families. In a previous study in adults with hemiplegia, most chose to aim for a 10% increase in activity of the affected arm with respect to baseline. For those without hemiplegia, the prompts will be simply based on baseline data.

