Activity levels will by necessity vary during the day and be different for school days and weekends. However, the ratio of the activity of the affected versus unaffected arm provides a method of modulating the prompts in a responsive manner for those with hemiplegia.

During the next 6 weeks, the personalised thresholds will be used to set prompts (visual and/or vibratory cues) through the wristbands for the children/young people to use their arm and hand if activity falls below the set threshold. It will be possible for a researcher to adjust the thresholds for prompts, through a webbased login, if necessary.

At the end of the day the children/young people will be encouraged to view the app to gain information regarding how much they managed to improve the activity of the affected arm. To provide motivation, this improvement will also be translated into reward points to use in a simple game they can play on the app.

During the final 2 weeks of the study the children/young people will not be given prompts or feedback: this will allow us to see if the increased level of activity can be maintained without this information.

The children/young people and families will have weekly contact with a member of the research team over the phone, via Skype or if needed face to face to troubleshoot and obtain feedback.

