6.2.6 Data analysis

Qualitative data: Analysis of the telephone interviews throughout the study will provide a large dataset in regards to the acceptability and the feasibility of the device and the app during the children's everyday life. The qualitative analysis will be conducted according to the standard procedures [24] including open and focused coding, constant comparisons and memoing [25], deviant case analysis [26], and mapping [27]. When analysing this data we will specifically explore the issue in regard to age and gender on the acceptability of the device/app, ease of use, fidelity and the perceived benefits of use.

Quantitative data: The data recorded from the accelerometer will be analysed to see if the prompts to increase arm activity were effective. The change in arm activity will be measured by a signal vector magnitude of overall arm movement for pre-specified periods of time including the hour before a prompt and the hour following a prompt. This data once analysed can be further categorised in terms of the level of arm use (e.g. if movements are light, moderate or vigorous) in comparison to the child's baseline threshold.

The level of change in arm activity is judged from the extent to which baseline measures do not overlap with those in the intervention phase (percentage of non-overlapping date) [28]. From the data collected from each of the participants a 10% increase in the relative arm use in the active monitoring period compared with baseline function will be considered a proof of principle that the approach can increase arm use in daily activities.

In addition to this the relationship between baseline AHA/Ad-AHA, ABILHAND-Kids and Tyneside Pegboard test scores and improvement in arm use will be explored.

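### The 10% proof-of-principle rule rests on one crude baseline-to-active contrast, so an uneven mix of school and non-school days can create or hide part of the change

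*Protocol*

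**What the plan says.** Section 6.2.6 of the protocol fixes the success rule: a rise in relative arm use of 10% "in the active monitoring period compared with baseline function will be considered a proof of principle that the approach can increase arm use". The companion measure, percentage of non-overlapping data, is judged from "the extent to which baseline measures do not overlap with those in the intervention phase". Both therefore compare baseline with the active phase only.

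The phases fall at the same point after first wear for every child. The study summary gives "Baseline (2 weeks): the device records arm activity without giving feedback", then six weeks of feedback, then two final weeks under baseline conditions. Section 6.1.4 explains the first phase: "The aim of the first 2 weeks is to obtain baseline data on activity levels for each young person". Of the final phase it says "this will allow us to see if the increased level of activity can be maintained without this information".

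On calendar variation, section 6.1.4 states: "Activity levels will by necessity vary during the day and be different for school days and weekends". It then offers the affected-to-unaffected arm ratio, but as a means of adjusting prompts. Section 6.2.6 does not say that relative arm use in the 10% rule is this ratio, and it also refers to signal vector magnitude of overall arm movement. School holidays are not mentioned, and the assessment schedules in section 6.2.4 list no record of day type.

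**The concern.** The protocol recognises that activity depends on the kind of day, yet its success rule compares two phase averages as if the mix of days were the same in both. Baseline is short: one holiday week is half of it but only a sixth of the active phase. A child whose baseline falls in a holiday and whose active weeks fall in term, or the reverse, has a difference between phases that owes nothing to prompts or feedback.

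The final two weeks could help to show this, but their stated purpose presupposes that the earlier rise came from the approach. A calendar shift that lasts into weeks 9 and 10 would then be read as maintained benefit. At stake is whether meeting or missing 10% can be attributed to the approach.

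**Working it through.** The protocol gives no figure to reproduce: the 20 children rest on qualitative saturation, and no size is given for the school-day difference.

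**Inputs from the protocol.** Baseline 14 days; active phase 42 days; criterion +10%.

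**Assumption.** Mean relative use is 1 on a non-school day and 1 + D on a school day, with D = 10%, 14% or 20% as an illustrative range. The approach has no effect.

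**Weekends alone.** Any 14 consecutive days hold 4 weekend days, and any 42 hold 12. Since 4/14 = 12/42 = 28.6%, the weekday/weekend mix is balanced under complete wear and cannot by itself produce a change.

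**General formula.** With school-day share s_B in baseline and s_A in the active phase, the false change is (1 + s_A·D)/(1 + s_B·D) − 1. A full-term phase has s = 10/14 = 30/42 = 0.714.

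| Situation | s_B | s_A | D = 10% | D = 14% | D = 20% |
|---|---|---|---|---|---|
| Both baseline weeks in holiday, active in term | 0 | 0.714 | +7.1% | +10.0% | +14.3% |
| One baseline week in holiday, active in term | 0.357 | 0.714 | +3.4% | +4.8% | +6.7% |
| Baseline in term, two of six active weeks in holiday | 0.714 | 20/42 = 0.476 | −2.2% | −3.0% | −4.2% |
| All in term, half the weekend wear lost in the active phase only | 0.714 | 30/36 = 0.833 | +1.1% | +1.5% | +2.1% |

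In the first row the formula reduces to 0.714 × D. For the second row at D = 14%: (1 + 0.714 × 0.14)/(1 + 0.357 × 0.14) − 1 = 1.100/1.050 − 1 = 4.8%. If use is higher out of school (D negative), the signs reverse; the first row becomes −7.1%, −10.0% and −14.3%, and a real rise could be hidden.

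**Effect of the definition.** Let the affected arm have activity 0.6 and the other arm 1.0, and multiply both by a common factor c. The ratio is 0.6c/1.0c = 0.6 for any c, so its change is 0%. Under the ratio definition, D counts only the part of the school/non-school difference that is not shared by the arms. Under a definition based on the affected arm alone, D is the whole difference.

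**Final phase.** A shift that continues into weeks 9 and 10 leaves active-v-final near zero and final-v-baseline raised. A maintained benefit gives the same pattern, so the day-type adjustment is needed beside these contrasts. A response to feedback that fades is separated poorly: with an assumed weekly decay factor d of 0.5 to 0.8, the share of the initial uplift left in weeks 9 and 10 is (d⁶ + d⁷)/2, or 1% to 24%. Activity then falls back much as it would after a true but unsustained effect.

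**The case against.** The strongest reply is that reaching a false 10% needs an extreme alignment: a baseline wholly in holiday, an active phase wholly in term, and D of at least 14%. One holiday week in baseline stays below 10% over the whole range. If relative arm use is the affected/unaffected ratio, D may be small. Section 6.2.6 also plans a contrast of the hour before with the hour after a prompt, which lies within the active phase and does not depend on the calendar mix. Day-type modelling could sit in an analysis plan that was not available for this review.

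Much of this stands, and it limits the point to a cheap improvement. It does not remove it. The success rule itself is fixed in the protocol, its outcome is undefined there, and a bias of 3% to 7% is large against a 10% threshold. The prompt-hour contrast is not part of that rule and is exposed to regression to the mean, because prompts fire when activity is low.

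A reader might infer more than the protocol supports:

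- **That novelty of the device can meet the criterion.** The devices are new during baseline. Extra activity then would raise baseline and work against a rise. A short-lived response to new feedback is still an effect of the approach.
- **That the buddies are an untreated reference.** Section 6.1.4 gives those without hemiplegia prompts based on their own baseline, and section 6.1.5 gives them the app.
- **That the study ignores the withdrawal weeks.** They have a stated use, maintenance; they are only outside the criterion.
- **That the switch-on day should be randomised.** This is a design preference, and it would break the whole-week balance shown above.

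**Conclusion.** The point holds in limited form. As written, the 10% rule is a single unadjusted contrast at a fixed time for every child, and an uneven school-day mix can create or hide part of the change. The size is 0.714 × D in the worst alignment (7% to 14% for D from 10% to 20%), 3.4% to 6.7% for one holiday week in baseline, and 1% to 2% for the uneven-wear example. All of these rest on an assumed D. They shrink to the differential change between arms if relative arm use is the affected/unaffected ratio. The protocol does not show that holidays will coincide with baseline, nor that most of the 20 children would share the same alignment, so it cannot be said that the study's overall conclusion would be false.

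**What to change.** In section 6.2.6:

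1. State that relative arm use in the 10% criterion is the affected/unaffected activity ratio.
2. Record each day as school or non-school, by one question in the existing weekly call.
3. Estimate the active-v-baseline change within school days and within non-school days, and standardise to a fixed 5:2 mix. Where a child's baseline has no school days, the school-day contrast cannot be estimated; report the non-school contrast and say so.
4. Report active-v-final and final-v-baseline from the same model beside the 10% criterion, so that a shift persisting after prompts stop is not automatically read as maintained benefit. Do not require a fall after withdrawal, since carry-over is possible.
5. Show the buddies' change over the same dates as descriptive calendar context only.

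The cost is one extra question a week, slightly more analysis, and less precision for children with few days of one type in baseline. Phase lengths and the intervention are unchanged.

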6.2.7 End of study

The end of the study (excluding analysis/writeup period) is defined as the point in time at which the last data item has been collected from the last participant.

6.3 Dissemination and Publication

Once the all of the data has been analysed and a conclusion has been drawn, the findings of the study will be disseminated to the children with HCP who took part in our study, along with their families and their buddies and therapists as a summary/leaflet. If the paper is published the children and their families will also be informed and once published they will be able to get a copy of this paper. We also intend for the results to be presented at a national or international conference. None of the participants of the study will be identifiable in the summary, the published paper or when the findings of the study are presented.

7 ETHICS

The study protocol and all of the required documentation will be submitted to the NHS Research Ethics Committee (REC). All other research approvals will be obtained before the study begins.

7.1 Ethical Considerations

Due to the study involving children who are under the age of 16 years there are ethical issues around consent, confidentiality and power relations. These will be handled sensitively. However, we believe that it is appropriate to undertake this research in children, because this is the only way to find out whether this

approach could benefit them in future. The approach has been specifically designed with this age group in mind, to be appealing and to help them develop independence in managing their own healthcare. Similar approaches (without the app) have been used in adults after stroke but this does not mean we can infer they are acceptable or likely to work in HCP.

7.1.2 Risks

When taking part in the study there is a risk that the children may experience fatigue and/or discomfort due to the increased level of activity of their affected arm when trying to reach their personalised threshold of movement. If this is the case we will set the child a lower threshold of activity to achieve if they choose to continue taking part in the study.

The wrist-worn devices are safe and should not pose any risk to the children. However there may be a risk that the children will find them uncomfortable, if they do find them uncomfortable we can try loosening the devices or changing the strap.

There are risks to children when using smartphones and having access to the internet. Parental safeguards/controls can be put in place, including on phones borrowed for use in this study. We will offer guidance into this including links to further information/advice on internet safety.

We will replace lost phones/devices within reasonable limits.

We will be open to recognise potential child safeguarding issues and follow them up as the law requires. Staff will have DBS checks in place. [name] and [name] are paediatricians.

We recognise that taking part in the study involves significant time and commitment but our long term goal is to allow the children to be able to incorporate the approach into their daily lives with minimum disruption.

There is no financial incentive for taking part in the research project, though children will receive a small gift voucher as a token of appreciation for their participation. Any travel costs incurred will be reimbursed to the families.

7.1.3 Systems for monitoring and reporting of adverse events

General definitions:

- Adverse event: This is any untoward medical occurrence there does not need to be a causal relationship between the occurrence and the study or any treatments administered.
- Serious adverse event: Any adverse event that
 - results in death
 - is life-threatening
 - requires hospitalisation or prolongation of existing hospitalisation
 - results in persistent or significant disability or incapacity
 - Consists of a congenital anomaly or birth defect.

7.1.3.1 Reporting an adverse event

Adverse/reportable events that occur have to be reported to the sponsor of the study under EU law.

7.1.3.2 Timeline of Reporting

The Chief Investigator will report:

- Immediately and no later than 2 calendar days after awareness of a SAE which indicates an imminent risk of death, serious illness and that requires prompt action for other patients / subjects, users or other persons;
- Immediately, but no later than 2 calendar days after awareness of a new reportable event or of new information in relation with an already reported event.
- Immediately, but not later than 7 calendar days following the awareness of any other reportable events or a new finding / update to a new reportable event or one which is already known.

7.1.4 Withdrawal from the study

If the parent(s) or the child decide that they no longer want to participate in the study they are free to withdraw at any time without having to provide a reason. This will not affect their normal NHS care or treatment. The data that will be collected from the participant up until this point will be retained and may still be used.

If one of the "buddy pair" drops out of the study, the other member of the pair can still remain in the study.

7.1.5 Informed consent

Fully informed written parental consent and assent from the young person will be obtained prior to participation. Therapists will also provide informed consent prior to any discussions (and following consent from the parents to approach the therapists). All parties will be given sufficient time to discuss the study, read the information sheets, ask questions and think about whether they want to take part, and will be made aware that they can change their mind at any time without any adverse consequences.

7.1.6 Funding and Sponsorships

The study is funded through Action Medical Research. The intended sponsor of the study is the Newcastle upon Tyne NHS Foundation Trust.

7.1.7 Indemnity and insurance

In the event of personal injury occurring on NHS premises or due to NHS treatment or negligence, professional and NHS insurance provides indemnity cover. In the event of injury occurring due to conduct of the research study, the Newcastle upon Tyne Hospitals NHS Foundation Trust provides indemnity cover. Newcastle University provides indemnity for the study design.

7.1.8 Anonymisation and data storage

All the data collected during the study will be stored on secure servers which are password protected. We will store patient identifiable information on Trust servers and use a patient study number to link this data to study data stored on secure university systems. In addition a hard copy will also be kept securely in a locked filing cabinet situated on Trust premises in a secure-access building. This is so that participants can be contacted in regards to follow up appointments/assessments. Personal data for participants who are not patients will be stored on secure university systems. Only appropriate members of the research team will have access to the files. The research data that is kept (both that on the computer and the hard copies) will be stored with a unique identification code. The Chief Investigator will maintain all of the stored data: this will include keeping documents updated and making any amendments necessary.

Any audio recordings that are collected during the study will be transcribed as soon as reasonably possible after the workshop. The originals will be destroyed once the project is completed for reference.

All data and audio recordings will be stored in accordance with the Data Protection Act 2018 and registered through the GDPR registrar.

7.1.9 General Data Protection Regulation (GDPR) Policy and Action in Event of a Breach

In the unlikely event of a breach in GDPR the relevant supervisory authorities will be made aware of the breach within 72 hours, where feasible. If the breach is likely to affect an individual personally, that individual will be informed without undue delay. If they feel it appropriate, they will be able to make a formal complaint through the NHS Complaints Procedure. If the breach is a result of negligence then participants may have grounds for compensation against Newcastle upon Tyne Hospitals NHS Foundation Trust, or the Evelina Children's Hospital.

References

- 1. Skold, A., S. Josephsson, and A.C. Eliasson, *Performing bimanual activities: The experiences of young persons with hemiplegic cerebral palsy.* American Journal of Occupational Therapy, 2004. **58**(4): p. 416-425.
- 2. A, J., *Prevalence and characteristics of children with cerebral palsy in Europe.* Developmental Medicine & Child Neurology, 2002. **44**(9): p. 633-640.
- 3. Goodman, R., *Psychological aspects of hemiplegia*. Archives of Disease in Childhood, 1997. **76**(3): p. 177-178.
